Aim 3. To evaluate the implementation of the intervention program across the 6 participating sites. The two primary implementation outcomes will be the number of implementation activities completed during the one-year active implementation period and the final level of team organization (defined as the Group Organization (GO Score)) for providing and improving TIA care at the end of the 12-month active implementation period. A covariate will include the degree of participation [Total # of calls attended/12 active implementation calls] in the monthly collaborative calls as noted in the call attendance. Implementation activities completed will be identified from multiple data sources: key updates and topics discussed during the collaborative calls; monthly action plan achievements and additional facilitator notes; the HUB implementation plan updates; and 6 and 12-month interviews. We hypothesize that sites that engage in ongoing [positive] implementation strategies of reflecting and evaluating, goal setting, and planning will realize the greatest implementation success (defined across the two primary implementation outcomes: number of implementation activities and the Group Organization (GO score)). We also hypothesize that sites with greatest implementation success will achieve the highest Without-Fail rate. We further plan to map implementation activities completed onto the key implementation strategies (reflecting and evaluating, goal setting, and planning) stratified by valence [positive & negative] based upon the mixed methodology coding.

Secondary Aim To evaluate the sustainability of the program. Sustainability will be evaluated over a one-year period that begins after the one-year active implementation period. We will compare the Without-Fail rate in the sustainability period to the post-implementation period. Our hypothesis is that sites that implement a facility-wide, TIA System of Care (reflected in a final 12-month GO score between 8-10) will demonstrate the greatest program sustainability as measured by the Without-Fail rate. Further, sites that maintain their implementation activities involving PREVENT-related program elements during the sustainability period will demonstrate the greatest program sustainability as measured by the Without-Fail rate.

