F	1/30/2017-1/30/2018	1/31-2/1/18	2/2/2018-4/12/2018	4/13/18	5/13/18-5/12/19	5/13/19-9/30/19

Primary Aim 2 Analysis:

Descriptive Analysis: The Without-Fail care rate will be estimated at each site for each of the three periods (baseline, post-implementation, and sustainability) to exam the temporal trends in the intervention effectiveness. The 95% confidence intervals for the rates will be provided.

Statistical Models: Due to the variation of sample size across the sites and across the implementation phases, generalized mixed-effects models (GLMM) at patient level with multilevel hierarchical random effects will be developed to analyze the intervention effects on the Without-Fail care rate during the post-implementation period and sustainability period compared with the baseline period.

The baseline data period is the one-year prior to the date of the baseline site visit. The active implementation phase data period extends for one year from month 2-13 after the Kick-Off event. For the primary effectiveness analysis, the main comparison is the mean facility Without-Fail rate across the six sites during the baseline data (control) period (blue shading above) versus the mean facility Without-Fail rate across the six sites during the post-implementation data period including the active implementation and one year after the active implementation phases (green and pink shadings above). We propose to model the “Without-Fail” care rate by

$$\log \frac{P(Y_{ij,k} = 1 | X_{ij,k}, Z_{ij,k}, W_{ij,k})}{1 - P(Y_{ij,k} = 1 | X_{ij,k}, Z_{ij,k}, W_{ij,k})} = \mu + \alpha_i + \beta_j + X_{ij,k}\theta + Z_{ij,k}\gamma + W_{ij,k}^t\tau$$

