Aim 3 Hypothesis B: that sites with greatest implementation success (based on the number of implementation activities completed and the level of team organization for providing and improving TIA care at 12 months) will achieve the highest Without-Fail rate. The measures of implementation success will be included in the GLMM model described above as cluster-level (aka facility-level) covariates. Specifically, the change in GO score from baseline to post-implementation as well as the number of implementation activities during the active implementation phase will be included in the model along with the covariate of the number of collaborative calls attended.

Example Table: Aim 3B

Site	PRIMARY IMPLEMENTATION OUTCOMES				Final Without-Fail Rate
	Number of Implementation Activities Completed	Number of Collaborative Calls Attended	Final GO Score Provide	Final Go Score Improve	
A					
B					
C					
D					

E					
F					

Aim 3 Secondary Implementation Analyses

Example Table: Aim 3C

Strategies Used	Final Without Fail Rate	
	High	Low
Reflecting (+/-)		
Goal Setting (+/-)		
Planning (+/-)		
Facilitation Dose		
Collaborative Calls (Dose)		
Use of Hub (Data Pages)		
Clinical Champion (scale rating)		
OCAI organizational profiles		

Identification of Effective Implementation Strategies

As described above, PREVENT employs three primary implementation strategies: (1) team activation via (a) audit and feedback, (b) reflecting and evaluating, (c) planning, and (d) goal setting; (2) external facilitation; and (3) building a community of practice. In addition, PREVENT allows for local adaptation of the intervention and also takes advantage of peer pressure. The identification of successful implementation strategies will be based on a mixed methods assessment where the change in the Without-Fail rate will be used to define implementation success. As shown in Table 3C, we will compare facilities based upon a High Final Without Fail rate as defined as 50% or higher compared to those defined as low final rate (less than 50%) by the degree of engagement in implementation strategies and dose received as well as strength of clinical champion and organizational culture. Similarly, we will compare the rate of change [% of change] from baseline to end of active implementation.

External Facilitation

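### The Hypothesis B model gives baseline encounters implementation values that arose only after Kick-Off, and it does not separate the overlapping active-year association from the time-ordered later one

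*Combined protocol and SAP*

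**What the plan says.** Section 2 (Aim 3) names two primary implementation outcomes. One is "the number of implementation activities completed during the one-year active implementation period"; the other is the final GO score, taken "at the end of the 12-month active implementation period". Call participation is a covariate, defined as "Total # of calls attended/12 active implementation calls".

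Section 4.3, Hypothesis B, predicts that the sites with the greatest implementation success will reach the highest Without-Fail rate. On the model it says "The measures of implementation success will be included in the GLMM model described above as cluster-level (aka facility-level) covariates". The first term is the change in GO score from baseline; in addition, "the number of implementation activities during the active implementation phase will be included in the model along with the covariate" of calls attended.

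The model referred to is the patient-level logistic mixed model of section 4.2. It covers three phases (baseline, active year, and the period after it), with a coefficient for each of the last two. On the outcome window, section 4.2 says "The active implementation phase data period extends for one year from month 2-13 after the Kick-Off event". Example Table 3B in section 4.3 ends with a final Without-Fail rate column whose period is not defined.

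**The concern.** An exposure should be attached only to patients who could have been affected by it. A covariate held constant within a site across all three phases is also attached to that site's baseline patients, who were treated before any activity, call or GO change took place. One coefficient then averages the site-level association over baseline, active year and later phase. The baseline part tells us how sites differed beforehand, not what implementation did.

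The active year raises a second, milder problem. Activities and calls build up while the outcome is being collected, and the final GO score is dated near the end of that window. Sites see their own process data on the Hub, so a rate that rose early could raise the organization recorded at month 12. A single coefficient cannot show which came first.

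At stake is the reading of Hypothesis B. The primary Aim 2 comparison is not affected.

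**Working it through.** **1. The outcome window against the site dates.** The inputs are the Kick-Off and data-period dates in the section 4.2 table. The active-year window should run from Kick-Off + 1 month to Kick-Off + 13 months − 1 day. It does so at all six sites, 365 days each, so the plan's months 2-13 are reproduced.

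**2. Days before the GO score date.** Month 12 is taken as Kick-Off + 12 months.

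| Site | Baseline days | Active-year days | of which before month 12 | Later-phase days |
|---|---|---|---|---|
| A | 367 | 365 | 334 | 416 |
| B | 367 | 365 | 334 | 401 |
| C | 367 | 365 | 334 | 317 |
| D | 366 | 365 | 335 | 303 |
| E | 366 | 365 | 334 | 267 |
| F | 366 | 365 | 335 | 141 |
| All | 2199 | 2190 | 2006 | 1845 |

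- Active-year days before month 12: 2006 / 2190 = 91.6%. If the score were taken at the end of month 13, this would be 100%.
- Baseline share of all modelled days: 2199 / (2199 + 2190 + 1845) = 2199 / 6234 = 35%.

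**3. Effect of attaching the covariates to baseline encounters.** In a logistic model with phase terms and one common slope, the pooled slope is approximately Σ wⱼbⱼ / Σ wⱼ. Here bⱼ is the slope in phase j and wⱼ = nⱼpⱼ(1 − pⱼ). The approximation ignores the site random effects. Assumptions: 25% Without-Fail at baseline and 50% in both later phases (the section 4.2 power statement), and equal encounters per phase.

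- Weight per encounter: 0.25 × 0.75 = 0.1875 at baseline; 0.50 × 0.50 = 0.25 afterwards.
- Baseline share of the weight: 0.1875 / (0.1875 + 0.25 + 0.25) = 0.1875 / 0.6875 = 27%.
- Pooled slope ≈ 0.27 × baseline slope + 0.73 × post-Kick-Off slope.
- With no baseline slope and an assumed true log-odds slope of 0.060: 0.060 × 0.727 = 0.044. Fitting the logistic model to expected rates under these assumptions gives 0.043.
- With calendar days in place of equal encounters: 0.25 × 4035 / (0.1875 × 2199 + 0.25 × 4035) = 1008.75 / 1421.06 = 0.71, an attenuation of 29%.

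**4. Overlap of the activity count with the active-year outcome.** The documents give no accrual pattern, so this is a range. With encounters spread evenly over 1 to 13 months after Kick-Off and even accrual over months 0 to 12, the mean share of a site's total that comes after an encounter is (1/12) ∫₁¹² (1 − t/12) dt = (1/12)(121/24) = 42%. So 58% is already in place. The share still to come is 17% if activities are all done evenly by month 6, 27% with front-loading (square-root accrual) and 58% with back-loading (squared accrual).

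**The case against.** A reader might go further and infer that most of the active-year outcome precedes the implementation said to cause it. The documents do not support that, for four reasons.

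- Activities and calls accrue during the same year. Under even or front-loaded accrual, most of a site's total is in place before the average encounter. The ordering argument applies only to the GO score.
- A scoring date is not the date on which organization began. Section 4.3 defines the GO score by practices sustained at a given time and builds it partly from monthly call updates, so the month-12 value may describe a state reached earlier.
- The model is not confined to months 2-13. Its later phase follows the measurement, and the Secondary Aim in section 2 already relates the 12-month GO score to later Without-Fail care.
- Hypothesis B predicts which sites will have the highest rate. It does not state causation in so many words.

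All four stand, and they limit the active-year point to overlap and possible reverse influence. They do not answer the baseline point.

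It can also be said that the covariate vector in the section 4.2 model carries a phase index, so an analyst could set the values to 0 at baseline. The notation allows this, but the text describes facility-level covariates and never says it will be done.

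Finally, a fully time-varying activity count is no clean cure. It rises with time since Kick-Off, overlaps strongly with the active-phase indicator, and the model has no calendar-time term. Restricting GO to the later phase alone keeps 1845 of 4035 post-Kick-Off data days (46%). Both are fair reasons not to make either one the sole analysis.

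**Conclusion.** The concern holds in a limited form. As written, implementation values that arose after Kick-Off are assigned to baseline encounters, and one coefficient blends three phases with different time ordering. If sites did not differ at baseline in relation to later implementation, the coefficient is attenuated by about 27% to 29%. This rests on the assumed 25% and 50% rates, equal encounters or calendar-day weights, and an approximation without site random effects. If sites did differ at baseline, the bias goes toward that difference and could have either sign.

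For the active year, the GO score is dated after 91.6% of the outcome days, so reverse influence through Hub feedback cannot be excluded. For activities and calls the finding is overlap only. The undefined period of the Table 3B outcome is an ambiguity to settle, not evidence of reversed timing.

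**What to change.** In section 4.3, Hypothesis B:

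1. Set the activity count, calls attended and GO change to 0 for baseline encounters; equivalently, enter them only as interactions with the active-phase and later-phase indicators. Centering each at its six-site mean first keeps the two phase coefficients interpretable for an average site.
2. Report the active-year and later-phase coefficients separately. Name the later-phase coefficient as the time-ordered test for GO, and label the active-year coefficients associational.
3. State which data period the final Without-Fail rate in Example Table 3B covers.
4. Where completion dates exist, add a sensitivity analysis with the cumulative number of activities completed by each encounter's date, noting that it tracks time since Kick-Off. The sponsor should first confirm that dates are recorded, because the plan does not specify them.

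Items 1 to 3 need only SAP wording and recoding. The price is precision. Site F has 141 later-phase days. At an assumed 30 to 50 patients a year (the range in the section 4.2 power text), that is 30 × 141/365 ≈ 12 to 50 × 141/365 ≈ 19 encounters. The 95% half-width at a 50% rate is then 1.96 × √(0.25/12) ≈ 28 points to 1.96 × √(0.25/19) ≈ 22 points. Splitting by phase also does nothing for the small number of sites: three covariates on six sites leave 6 − 1 − 3 = 2 site-level degrees of freedom in each phase. The results should be presented with that limit stated.

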4.4 Secondary Aim Methods (Sustainability)

The sustainability analysis will include: a comparison of the change in the Without-Rail rate from the baseline data period to the sustainability period (blue versus pink shading above). We will build multilevel models as described above for the Aim 2 analysis as described above.

We will explore whether sites with the greatest use of their own quality data (e.g., did they generate their own data, the frequency with which they reviewed the process of care data on the hub, whether they incorporated process of care data into routine work flow, did they conduct their own chart reviews) demonstrate the greatest program sustainability. Again, these cluster-level characteristics will be included in the GLMM model described above.

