where i indexes the site ($i = 1, 2, 3, 4, 5, 6$); j the implementation phase (1: baseline period; 2: active implementation phase; 3: one year after the active implementation phase); k the encounter at the i^{th} site and the j^{th} phase ($k = 1, 2, \dots, n_{ij}$); n_{ij} is the total number of encounters at the i^{th} site and the j^{th} phase; $X_{ij,k}$ and $Z_{ij,k}$ the indicators of the active implementation phase and one year after the active implementation phase, respectively; $W_{ij,k}$ the vector of the k^{th} encounter's characteristics at the i^{th} site and the j^{th} phase that could include the site characteristics; $Y_{ij,k} = 1$ the indicator of observation of “Without-Fail” care process on the k^{th} encounter at the i^{th} site and the j^{th} phase. For this model, μ represents the average log odds of Without-Fail care across the 6 sites at baseline; θ the log odds ratio between the active implementation phase and the baseline indicating the intervention effect during the active implementation phase; and γ the log odds ratio between one year after the active implementation phase and the baseline indicating the intervention sustainability effect post the implementation; α_i and β_j are the site and phase specific random effects that are assumed to be multivariate normal. After fitting the model, the normal theory can be applied to test the intervention effect at the active implementation phase and the intervention sustainability effect.

Secondary Aim 2 Analyses: Several secondary effectiveness analyses are planned.

Comparison to Matched Controls

Six control sites will be matched to each of the six PREVENT active implementation sites on the basis of: TIA patient volume, facility complexity (i.e., teaching status, intensive care unit level), and quality of care (measured by the without-fail rate). The total number of control sites will be 36. The definition of the baseline period (the specific start and end dates of the one-year baseline period) for each matched control site will be identical to the definition used for the PREVENT active site to which the controls are matched. We will compare changes in quality and outcomes at control sites to changes at PREVENT sites as a method for assessing temporal trends.

Changes in Individual Processes of Care

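### The Secondary Aim asks whether the active-year gain was kept, but the methods specify only sustainability versus baseline, over a window that is not the stated one year

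*Combined protocol and SAP*

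**What the plan says.** **The aim (section 2, Secondary Aim).** "We will compare the Without-Fail rate in the sustainability period to the post-implementation period". On timing: "Sustainability will be evaluated over a one-year period that begins after the one-year active implementation period".

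**The methods for that aim (section 4.4).** The analysis is to include "a comparison of the change in the Without-Rail rate from the baseline data period to the sustainability period (blue versus pink shading above", where the misspelt outcome is evidently the Without-Fail rate. The models are those of Aim 2.

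**The Aim 2 model (section 4.2, Primary Aim 2 Analysis).** Its purpose is to assess effects "during the post-implementation period and sustainability period compared with the baseline period". Phase 3 is labelled "3: one year after the active implementation phase". Theta is the log odds ratio of active implementation against baseline. Gamma is "the log odds ratio between one year after the active implementation phase and the baseline indicating the intervention sustainability effect post the implementation". The tests are stated thus: "the normal theory can be applied to test the intervention effect at the active implementation phase and the intervention sustainability effect". The alpha and beta terms "are the site and phase specific random effects that are assumed to be multivariate normal".

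**The data periods (section 4.2, Effectiveness Data Period Definitions).** Sustainability runs from month 14 after the Kick-Off to 9/30/19 at every site, and the table itself calls this variable. The Design paragraph of 4.2 describes a sustainability phase lasting a year or more.

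**Descriptive output.** Section 4.2 calls for site rates with 95% CIs in all three periods. Table 4 sets the periods side by side, unadjusted and without a p-value column.

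**The concern.** Two different questions share one name. Sustainability against baseline asks whether care is still better than usual care. Sustainability against active implementation asks whether the improvement was held once active support ended, and that is the comparison the aim states. The plan attaches the label of sustainability effect to gamma, the first of these. A report that follows the plan could therefore announce a sustainability effect after much of the gain had gone.

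The window adds a second misdescription. Gamma would be presented as the effect over the year after active implementation, when at site F it rests on less than five months of data.

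**Working it through.** **1. Contrasts, side by side**

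| Place | Comparison for the sustainability period |
|---|---|
| Section 2, Secondary Aim | versus post-implementation |
| Section 4.4 | versus baseline |
| Section 4.2, purpose of the model | versus baseline |
| Section 4.2, gamma and its test | versus baseline |
| Table 4 | side by side, no estimate or test |

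With theta = active minus baseline and gamma = sustainability minus baseline on the log-odds scale, the aim's contrast is gamma − theta, with variance Var(gamma) + Var(theta) − 2 Cov(gamma, theta). It is not named anywhere.

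**2. Can it be read from the model as written?** The fixed part for phase is an intercept and two indicators, one parameter for each of three phases. Over the 18 site-by-phase cells (6 × 3) these columns have rank 3. Adding the three columns of the phase random effect leaves the rank at 3, so 3 − 3 = 0 degrees of freedom remain for its variance. The point estimate of gamma − theta is unaffected, but its variance gains a term 2σ²(beta) that the data cannot estimate. A site-by-phase random effect would be estimable: phase and site together have rank 3 + 5 = 8, leaving 18 − 8 = 10 degrees of freedom.

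**3. Length of the window.** The stated figure is one year. Inclusive day counts from the table, with months = days / 30.4375:

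| Site | Start | End | Days | Months |
|---|---|---|---|---|
| A | 8/11/18 | 9/30/19 | 416 | 13.7 |
| B | 8/26/18 | 9/30/19 | 401 | 13.2 |
| C | 11/18/18 | 9/30/19 | 317 | 10.4 |
| D | 12/2/18 | 9/30/19 | 303 | 10.0 |
| E | 1/7/19 | 9/30/19 | 267 | 8.8 |
| F | 5/13/19 | 9/30/19 | 141 | 4.6 |

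The total is 1,845 site-days. The active period is 365 days at all six sites (2,190), and baseline totals 2,199. One year is not reproduced: two sites exceed it and four fall short.

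**4. Illustration (assumed inputs).** Take 30 or 50 TIA patients per site-year (the two volumes in Power and Sample Size), 25% at baseline and 50% in the active year. Numbers are volume × site-days / 365.25: baseline 181 / 301, active 180 / 300, sustainability 152 / 253. The 18 cell logits are fitted by generalised least squares with cell variance 1/(n p (1 − p)), an assumed site SD of 0.5, and an assumed site-by-phase SD of 0, 0.2 or 0.4. Tests are two-sided at 5%, with a normal reference at SD 0 and t with 10 df otherwise.

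Probability of significance if half the gain is lost (sustainability 37.5%), at 30 / 50 per site-year:

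| Site-by-phase SD | versus baseline | versus active |
|---|---|---|
| 0 | 0.68 / 0.88 | 0.62 / 0.83 |
| 0.2 | 0.51 / 0.67 | 0.44 / 0.59 |
| 0.4 | 0.35 / 0.43 | 0.30 / 0.35 |

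If the rate falls only to 40%, the aim's odds ratio is (0.40/0.60)/(0.50/0.50) = 0.67. Its expected 95% CI is:

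| Site-by-phase SD | 30 per site-year | 50 per site-year |
|---|---|---|
| 0 | 0.43 to 1.04 | 0.47 to 0.94 |
| 0.2 | 0.38 to 1.17 | 0.42 to 1.06 |
| 0.4 | 0.32 to 1.37 | 0.35 to 1.27 |

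**5. First-event rule.** Section 4.2 (Sensitivity Analyses) limits the primary analysis to each patient's first TIA in the whole study. If that carries over and removes an assumed 20% of sustainability patients, numbers fall from 152 to 121 (253 to 202). With half-width = 1.96 × √(p₁(1 − p₁)/n₁ + p₂(1 − p₂)/n₂), patients treated as independent, the interval for a fall from 50% to 40% widens from ±10.7 to ±11.4 points (±8.3 to ±8.8).

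**The case against.** The strongest reply is that this is a gap in wording. Section 4.4 lists what the analysis will include and excludes nothing, section 2 already commits to the other comparison, and one model yields both phase effects. A large fall would also be visible, since rates with CIs are reported by site and period. Nor is a significant result against baseline at 37.5% false: a real 12.5-point gain would remain. All of this is fair. What it leaves missing is an estimate and interval for the difference the aim names.

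The phase random effect touches theta and gamma equally, so it is not peculiar to sustainability. In a linear mixed-model check on simulated cells, the point estimate of gamma − theta did not move with the assumed SD of that effect, and maximum likelihood favoured an SD of zero. Under REML, however, the likelihood was flat and the standard error grew with the assumed SD. The interval for the aim's contrast would thus depend on the estimation method.

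The table does give exact dates, so the data cut is not in doubt; the one-year description is what fails. The Design paragraph may describe a project phase rather than a data window, and needs only clarification.

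The aim's contrast is also not the more powerful one: in the 37.5% case it trails the baseline contrast throughout. The case for it is that it answers the stated question.

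**Conclusion.** The concern holds on both parts, and the plan should be changed. The methods for the Secondary Aim answer a different question from the one the aim poses, and the model calls the answer a one-year sustainability effect when the data cover 4.6 to 13.7 months depending on site.

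The mismatch of contrasts, the day counts (two of six sites reach 365 days) and the zero degrees of freedom for the phase random effect follow from the documents without assumption. The powers and intervals in steps 4 and 5 rest on assumed rates, volumes, variance components and patient loss. They show scale only, and the conclusion does not depend on them.

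**What to change.** 1. In section 4.4, name sustainability versus active implementation (months 2 to 13 after the Kick-Off) as the aim's contrast, estimated as gamma − theta with a 95% CI. Keep sustainability versus baseline as supportive. Stating the months matters because one sentence in 4.2 extends the post-implementation period over the following year as well, which would overlap the sustainability period.
2. Remove the phase random effect, or replace it with a site-by-phase random effect (10 df), and say in advance which. The choice affects the width of the interval.
3. Interpret the contrast by its estimate and CI, and state that a non-significant difference does not show the gain was sustained.
4. State whether the rule of one first TIA per patient applies here.
5. In section 2 and the model definition, restate the window as month 14 after the Kick-Off to 9/30/19 (4.6 to 13.7 months by site) and relabel phase 3 to match. Clarify how the phase in the Design paragraph relates to it.

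The cost is wording, one random-effect term and one contrast, with no new data. On the rate scale the aim's contrast is slightly less precise than the baseline one: ±10.7 against ±10.0 points at 30 per site-year with a 40% sustainability rate. A 10-point loss may therefore be inconclusive. The pooled contrast also does not test the aim's site-level hypotheses about GO score and maintained activities.
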